6.6 Method of Assigning Subjects to Treatment Groups

Following confirmation of eligibility, at study drug administration, subjects will be assigned a subject number in the order in which they are enrolled in the study, as shown in Table 6.1. The subject number will determine the allocation of treatment.

Table 6.1 Assignment of Subjects to Treatment

Study Part	Dose Level(s)	Subject Numbers
A	1, 2, 3	[REDACTED]
	4	[REDACTED]
	5	[REDACTED]
	6	[REDACTED]
	7	[REDACTED]
	Additional ¹	[REDACTED]
B	1	[REDACTED]
	2	[REDACTED]
	3	[REDACTED]
	Additional ¹	[REDACTED]

¹ eight additional cohorts of up to 6 subjects in Part A (up to an additional 48 patients) and three additional cohorts of up to 8 subjects in Part B (up to an additional 24 patients) may be enrolled in each part if agreed by the Safety Committee.

Any replacement subjects will receive the same treatment allocation as those whom they replace.

CONFIDENTIAL

Synoptic Clinical Study Protocol
Version 2.0 - 05/08/2017

EudraCT Number: 2017-000380-33

Subjects who are replaced (dropouts or replacements for subjects who are withdrawn from Cohort 1) will be allocated the same treatment number with the number 1 in the second digit position, e.g., if subject number [REDACTED] is replaced then the replacement subject's number will be [REDACTED].

6.7 Randomisation Procedures

Allocation to treatment will be according to a predetermined random order. Randomisation of Y14 or placebo will take place for each group separately. In Part A (SAD), each pair of sentinel subjects in Cohort 1 will be randomised such that 1 subject receives Y14 and 1 receives placebo.

The randomisation list will be generated by Covance using the statistical analysis system (SAS[®]) computer package.

6.8 Maintenance of Randomisation Codes

Randomisation codes will be provided to the pharmacist and bioanalyst in a list. Individual treatment disclosure envelopes (code break) will also be provided to the clinical unit. The pharmacist will use the randomisation code list for preparing subject doses throughout the study. The individual disclosure envelopes will be used if it is necessary to break the blind for an individual subject.

6.9 Blinding

Part A (SAD) will be conducted double-blind (with the exception of Cohort 1 where the volunteers taking the 3rd and 4th injections within a treatment period are guaranteed to be given Y14); subjects and clinical staff will remain blinded until the Safety Committee meeting.

Part B (MAD) will be conducted double-blind. In the event of a medical emergency when management of a subject's condition requires knowledge of the trial medication, the sealed "code-break" envelope provided may be opened by personnel authorised by the Principal Investigator to determine the nature of the trial medication dispensed. If possible, such emergencies should be discussed with the study monitor and the Sponsor's safety manager prior to disclosure of the treatment allocation. Reasons for breaking a code must be clearly explained and justified in the CRF. The date on which the code was broken together with the identity of the person responsible must also be documented.

The bioanalyst and the PK scientist who will be unblinded, will be required to provide coded data to the Principal Investigator and the Sponsor so that the blind is maintained for all other personnel connected with Part B of the study.

With the exception of the CRO pharmacy department, the statistician preparing the randomisation, the bioanalytical assay group and the quality assurance auditors where necessary, all clinical and non-clinical staff, with the exception of the PK scientist and PK/PD statistician, will remain blinded to the treatment allocation (where applicable) until after the database is locked unless there is a medical event that requires code break.

CONFIDENTIAL

Synoptic Clinical Study Protocol
Version 2.0 - 05/08/2017

EudraCT Number: 2017-000380-33

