signs, ECGs, and clinical laboratory safety tests), and tolerability (adverse event profile) data up to and including 24 h postdose will be reviewed by Covance's clinical team prior to dosing the remaining subjects at that dose level. Dosing of the subsequent subjects in cohort 1 will be at the discretion of the Principal Investigator.

Treatments will be administered double blinded (except for Cohort 1, TP1 where it will be known that the 3rd and 4th subjects will receive the active dose); subjects will be blinded with regard to treatment and clinical staff will remain blinded with regard to treatment until the Safety Committee meeting.

An interval of at least 7 days will separate the dosing of the last subject in one cohort and dosing of the first subject in the next cohort to permit a timely review and evaluation of interim safety, tolerability and PK data. Safety, tolerability and PK data will be reviewed up to 48 hours post-dose prior to the dose escalation decision. If T_{max} is significantly later than predicted, PK data to a later timepoint may be reviewed prior to the dose escalation decision. The data of up to at least 3 subjects receiving Y14 in cohort 1 and 4 subjects, (i.e. a minimum of 3 subjects receiving Y14) in cohort 2 onwards will be reviewed before dose escalation.

Following a 28-day screening period eligible subjects will be admitted to the clinical unit on Day -1 (1 day prior to dosing) for eligibility checks and baseline assessments. On Day 1 subjects will receive a single dose of Y14 or placebo by SC injection, and will remain in the clinical unit under medical supervision until 72 h postdose (Day 4) or until C_{max} is achieved, whichever is the later.

Safety monitoring will include assessment of adverse events (AEs), physical examination, 12-lead ECGs, vital signs (blood pressure pulse rate and body temperature) and clinical laboratory safety tests (serum biochemistry, haematology, coagulation, thyroid stimulating hormone [TSH], FT4 and urinalysis).

Blood samples for biomarker (tryptase) will be collected immediately after any possible allergic or anaphylactic adverse reaction, and 12 hours later. These samples will only be analysed if relevant adverse reactions occur.

The PK evaluation will include measurement of plasma Y14 levels and associated PK parameters.

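### Section 6.9 makes two injections known active in every Cohort 1 treatment period, whereas 5.1.1 confines this to the first; the end of the Part A blind also needs a precise rule

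*Combined protocol and SAP*

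**What the plan says.** **Which Cohort 1 doses are known to be active.**

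- Section 5.1.1 describes one sentinel pair, in Cohort 1 TP1, with one subject on Y14 and one on placebo. The third and fourth subjects in that period are known to receive Y14.
- Table 5.1 shows no sentinel subjects in TPs 2-3, where three Y14 subjects and one placebo subject form a single dosing session.
- Section 5.1.5 names Cohort 1 TP1 as the partially blinded exception.
- Section 6.9 states the exception for Cohort 1 as a whole: "volunteers taking the 3rd and 4th injections within a treatment period are guaranteed to be given Y14".
- Section 6.7 says that "each pair of sentinel subjects in Cohort 1 will be randomised" one to Y14 and one to placebo, which suggests more than one pair.

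**When the Part A blind ends.**

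- Section 6.9: "subjects and clinical staff will remain blinded until the Safety Committee meeting". Section 5.1.1 gives the same end point for staff only: "clinical staff will remain blinded with regard to treatment until the Safety Committee meeting".
- The last paragraph of 6.9 says that clinical and non-clinical staff, apart from listed roles, "will remain blinded to the treatment allocation (where applicable) until after the database is locked". It follows two paragraphs on Part B but is not expressly limited to Part B.
- On timing, 5.1.1 says: "Safety, tolerability and PK data will be reviewed up to 48 hours post-dose prior to the dose escalation decision". It sets at least 7 days between the last subject of one cohort and the first of the next, and a follow-up visit 14 ± 1 days after the final dose.

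**The concern.** Sections 6.7 and 6.9 are the operative text for randomisation and blinding. A pharmacist or statistician working from 6.9 would keep placebo off the third and fourth injections in all three periods. One working from 5.1.1 and Table 5.1 would do so only in TP1. The two readings give different lists and different degrees of blinding for the same four subjects.

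The end of the blind matters because adverse events are part of the primary variable (10.1). Their intensity (7.3.3) and relatedness (7.3.4) are judgements, and relatedness enters a stopping criterion in 5.1.4. Events are recorded throughout the study, so those arising between the committee meeting and follow-up could be reported, graded or attributed by people who know the allocation.

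**Working it through.** **Step 1: reproduce the plan's counts (5.1.1, Table 5.1).**

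- Part A enrolment: 4 + 4 × 6 = 28, as stated.
- Cohorts 2-5: 4 × 5 = 20 on Y14 and 4 × 1 = 4 on placebo, as in Table 5.1.
- Cohort 1: 4 subjects × 3 TPs = 12 dosing occasions, of which 3 × 3 = 9 are Y14 and 3 × 1 = 3 are placebo.

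**Step 2: count Cohort 1 Y14 doses known active before injection.** Known-active doses = (guaranteed-active positions per period) × (periods to which the guarantee applies).

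| Reading | TP1 | TP2 | TP3 | Known active |
|---|---|---|---|---|
| 5.1.1, with 5.1.5 and Table 5.1 | 2 | 0 | 0 | 2 × 1 = 2 of 9 |
| 6.9 taken literally | 2 | 2 | 2 | 2 × 3 = 6 of 9 |

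In TPs 2-3, Table 5.1 lets placebo fall on any of four dosing positions, subject to the rule in 5.1.1 that a different subject receives it each time. Under 6.9 it can fall on only the first two. This step assumes nothing about disclosure.

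**Step 3: time from the meeting to follow-up.**

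- Earliest follow-up: 14 − 1 = 13 days after the final dose. Latest: 14 + 1 = 15 days.
- Earliest meeting: about 2 days after the last subject's dose, because 48 h data are reviewed.
- Latest meeting, if the next cohort is dosed at the 7-day minimum: 7 days after that dose.
- Smallest gap for the last-dosed subject: 13 − 7 = 6 days. Largest: 15 − 2 = 13 days.
- Optional visits under 5.1.1 may run to 8 weeks (56 days) after the final dose. The gap to the latest such visit would be 56 − 7 = 49 to 56 − 2 = 54 days.

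The 7 days is a minimum with no upper limit. A longer interval could shrink the gap or remove it.

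**Step 4: compare the two statements on the end of the blind.** Sections 5.1.1 and 6.9 agree on the committee meeting for Part A clinical staff. The lock sentence sets a later end for clinical staff generally, qualified by its own parenthesis about applicability. If it covers Part A, it conflicts with the meeting rule; if it does not, there is no conflict. The text does not say which.

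**The case against.** The strongest reply is that most of this is design choice or loose drafting. A calendar date cannot be fixed in adaptive escalation, and 5.1.1 brackets the review: after 48 h data and before the next dose level. From Cohort 2 each subject is dosed once, so nothing learned at the meeting can affect his dosing or the 48 h data already collected. Allocation is 3:1 or 5:1, so assessors already expect active drug. The safety analysis in 10.6 is descriptive. All of this stands, and it is why the end of the blind is the secondary point. None of it resolves the difference between 6.9 and 5.1.1 on TPs 2-3.

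Some stronger readings are tempting but not supported:

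- *The plan unblinds Part A at the meeting.* No passage says that codes are opened or subjects told there. Section 6.8 gives the unit individual envelopes only: "The individual disclosure envelopes will be used if it is necessary to break the blind for an individual subject". The text permits early disclosure; it does not schedule it.
- *The lock sentence contradicts the Part A rule.* Its position after the Part B paragraphs and its qualifier allow a reading limited to Part B. This is ambiguity of scope, not a proven conflict.
- *Section 6.7 contradicts 5.1.1 on known-active injections.* It mentions neither such injections nor treatment periods. It points towards the 6.9 reading by implication only.
- *Further Cohort 1 doses become known because a different subject takes placebo each time.* That needs allocations to be disclosed between periods and no replacements. The first is not stated, and 5.1.1 provides for replacing dropouts, so these doses are not counted.
- *PK data leak the allocation.* The coding sentence in 6.9 does protect the blind only for "so that the blind is maintained for all other personnel connected with Part B of the study" in its scope, that is, Part B. But the Part A staff blind already ends at the meeting where PK is reviewed, so this adds little.

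**Conclusion.** The contradiction over Cohort 1 is real and follows from the text alone: 6 of 9 planned Y14 doses known active before injection under 6.9, against 2 of 9 under 5.1.1. It affects both the randomisation and the blinding of TPs 2-3. Section 6.7 should be corrected with 6.9, although it conflicts only by implication.

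The end of the Part A blind is a real but smaller weakness. At the 7-day minimum interval, the meeting precedes the last-dosed subject's follow-up by at least 6 days. This exposes judged adverse events only if allocations are actually disclosed at the meeting, which the protocol neither plans nor prevents. The documents give no basis for estimating how many events would be affected. Laboratory, ECG and vital-sign data depend less on judgement. The point should be fixed, but it does not undermine the study.

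**What to change.** 1. In 6.9, limit the guaranteed-active exception to Cohort 1 TP1. In 6.7, refer to the single TP1 sentinel pair. Placebo in TPs 2-3 can then fall on any dosing position, subject to the different-subject rule. Check that the randomisation list agrees. This aligns the blinding text with 5.1.1, 5.1.5 and Table 5.1; it takes no position on the clinical need for sentinel dosing.
2. State in 6.9 whether the database-lock sentence applies to Part A.
3. In 5.1.1 and 6.9, keep subjects blinded until their last follow-up (Cohort 1: after the TP3 follow-up), apart from emergency code breaks. Apply the same rule to site staff who grade or attribute adverse events and do not need allocations for the escalation decision.

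The first two changes are wording only and cost nothing. The third has a small cost. The Principal Investigator or a delegate is a required committee member under 5.1.3, and the protocol does not say who assesses relatedness. Either the escalation review uses group-level or coded data, or that member is acknowledged as an exception. No sample size, dose or assessment changes.

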7 STUDY PROCEDURES

The blood volumes to be collected from each subject are detailed in Table 7.1 for Part A (SAD) and Table 7.2 for Part B (MAD). The total volume to be collected per subject will be no greater than 600 mL, staggered over the duration of the study. No more than 15% of the estimated blood volume of a subject will be taken on any one occasion as per JPAC guidelines (<http://www.transfusionguidelines.org/>).

Laboratory sample handling details will be presented in a separate laboratory manual.

Table 7.1 Blood Volumes: Part A (SAD)

Cohort 1

Assessment	Sample Volume (mL)	No. of Samples	Total Volume (mL)
Safety			
Serum Biochemistry, Thyroid Function	3.5	11	38.5
Serology	3.5	1	3.5
Coagulation	1.8	11	19.8
Haematology	4.0	11	44
Tryptase ¹	3.5	2	7
Bedside blood glucose	0.1	Up to 23	2.3
Pharmacokinetic			
Y14	6.0	Up to 17	102
Pharmacodynamics			
Immunogenicity ³	6.0	2	12.0
Total²			229.1

¹ In the event of an allergic reaction additional samples will be collected.

² Sample volumes are based on direct venepuncture

³ Immunogenicity samples from cohort 1 only

CONFIDENTIAL

Synoptic Clinical Study Protocol
Version 2.0 - 05/08/2017

EudraCT Number: 2017-000380-33

Cohort 2 onwards

Assessment	Sample Volume (mL)	No. of Samples	Total Volume (mL)
Safety			
Serum Biochemistry, Thyroid Function	3.5	5	17.5
Serology	3.5	1	3.5
Coagulation	1.8	5	9.0
Haematology	4.0	5	20.0
Tryptase ¹	3.5	2	7
Bedside blood glucose	0.1	Up to 11	1.1
Pharmacokinetic			
Y14	6.0	Up to 17	102.0
Total²			160.1

¹ In the event of an allergic reaction additional samples will be collected.

² Sample volumes are based on direct venepuncture.

Table 7.2 Blood Volumes: Part B (MAD)

Assessment	Sample Volume (mL)	No. of Samples	Total Volume (mL)
Safety			
Serum Biochemistry including Thyroid function (TSH, FT4)	3.5	16	56.0
Serology	3.5	1	3.5
Coagulation	1.8	16	28.8
Haematology	4.0	16	64.0
Tryptase ¹	3.5	2	7.0
Bedside glucose monitoring	0.1	54	5.4
Pharmacokinetic			
Y14	6.0	37	222.0
Pharmacodynamics			
Immunogenicity	6.0	2	12.0
Oral glucose tolerance test glucose and insulin levels	3.5	21	73.5
Enteropancreatic hormones (GLP-1, PYY, ghrelin, leptin)	5.0	21	105
Total²			577.2

¹ In the event of an allergic reaction additional samples will be collected.

² Sample volumes are based on direct venepuncture

CONFIDENTIAL

Synoptic Clinical Study Protocol
Version 2.0 - 05/08/2017

EudraCT Number: 2017-000380-33

7.1 Pharmacokinetic Assessments

7.1.1 Plasma Samples

Blood sample collection times are included in the schedule of events.

Details of how samples will be collected, processed and stored will be included in a separate laboratory manual.

Bioanalysis

The bioanalysis will be performed by [REDACTED]. They will be responsible for the GLP validated bioanalysis, which will utilise a high performance liquid chromatography-tandem mass spectrometry (LC-MS/MS) assay in human plasma.

Any remaining plasma may be sent to the sponsor for analysis of Y14 using an exploratory non-GLP compliant, non-validated radioimmunoassay.

7.2 Pharmacodynamic/Efficacy Assessments

Time points for collection of PD variables are included in the schedule of events.

7.2.1 Visual Analogue Scales

Assessments of nausea and satiety will be performed using VAS. Subjects will be requested to rate their responses to a series of questions on a VAS from 0 to 100 mm.

7.2.2 Energy Intake

Energy intake will be recorded for Part A and Part B.

A formal 24 h food intake study will be carried out on Part A from Cohort 3 onwards, on Day -1 (measuring lunch and dinner on Day -1 and breakfast on Day 1) and Day 1 (measuring lunch and dinner on Day 1 and breakfast on Day 2).

For Part B, the food intake studies will be carried out on Days -1, 2, and 30. The food intake study on Day -1 will measure the ad libitum intake of food during breakfast, lunch and dinner on Day -1. The food intake study on Day 2 will measure the ad libitum intake of food during breakfast, lunch and dinner on Day 2. The food intake study on Day 30 will measure the ad libitum intake of food during breakfast, lunch and dinner on Day 30. The timing of the food intake study will be altered according to emerging PK data, if the t_{max} is delayed beyond 24 hours. If the timing of the food intake studies are changed the times of the OGTT samples may also be changed to ensure they do not happen on the same day.

While resident in the clinical unit during 24 h food intake assessment days, subjects will be individually provided meals in a designated area with individual cubicles per subject. Meals will be presented with an excess of food and subjects will be asked to eat until they feel "comfortably full" within a period of 30 minutes. Should a volunteer require more time to eat, an extra 15 minutes will be allowed, but such an event will be recorded as a deviation from protocol. The energy value of each component of the meal will be determined. Food will be weighed pre- and post-meal to determine consumption.

CONFIDENTIAL

Synoptic Clinical Study Protocol
Version 2.0 - 05/08/2017

EudraCT Number: 2017-000380-33

For other days in Part A and Part B, energy intake will be carried out semiquantitatively i.e. clinical research unit staff will record the timing, types and amounts of food eaten by subjects. For the semiquantitative measurement, at the end of each meal the percentage of food left will be assessed to be either <10%, 10-<25%, 25-<50% or ≥50%. Snack boxes will also be provided at certain timepoints whilst resident in the clinical unit (to be specified in the Meal Manual).

In Part B, subjects will be admitted on Day -2 (2 days prior to dosing) in order to acclimatise to the clinical research unit and obtain baseline food consumption measurements.

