5.1.3 Safety Committee

The Safety Committee's membership will be composed of a minimum of the Sponsor team (Sponsor Senior Physician and Sponsor Senior Scientist or an appropriate delegate) and Principal Investigator (or an appropriate delegate). Additional members may be invited as needed (e.g. PK scientist, project manager).

All data reviewed at the dose escalation meeting (safety, tolerability and available PK data) will be subjected to a quality control review.

CONFIDENTIAL**5.1.4 Stopping Rules**

Dosing for any individual subject will be stopped if the subject experiences a possibly drug-related serious adverse event or a possibly drug-related significant non serious adverse event, which in the opinion of the study physician, Principal Investigator or Chief Investigator (Sponsor's medical representative), warrants discontinuation of the study for that subject's well being.

In Parts A and B, following consultation with the Sponsor, dose escalation will stop if:

- Clinically relevant signs or symptoms of similar nature, occur in 2 or more subjects within a group/cohort, which in the opinion of the Investigator warrant stopping of dose escalation.
- A serious adverse event (SAE) in one or more subjects thought to be related to the study drug or a severe AE in two or more subjects thought to be related to study drug. If this criterion is met the study will be halted. If, following internal review, it is deemed acceptable to restart the study a substantial amendment will be submitted to the Competent Authority.
- Moderate nausea or vomiting that prevent subjects from eating a meal on 3 or more occasions on 2 successive days are seen in 2 or more subjects in a group.
- Severe diarrhoea, defined as 7 or more episodes, rated as ≥ 5 on the Bristol Stool Chart, in 1 day for 2 consecutive days are seen in 2 or more subjects in a group.
- The mean systemic exposure is predicted to exceed a C_{max} of 440 ng/mL and/or $AUC(0-72h)$ of 28,100 ng·h/mL i.e. systemic exposure will be no greater than that the lowest exposure at the NOAEL for male rats (30 mg/kg/dose). This limit is chosen on the basis that rats are expected to be the species that will most closely predict toxicity in humans.

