9.2.2 Energy Intake

The energy value per unit of weight will be determined for each individual component of a meal. Each component of the meal will be weighed pre and post-meal and the weight consumed will be calculated (i.e. weight pre meal - weight post meal = weight consumed). Total energy intake will be calculated from the weight of each component consumed.

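### On Part B dosing days, throughout Part B stays 2–4 and in Part A Cohorts 1–2, intake is recorded in bands whose top category (≥50% left) does not separate a half-eaten meal from an uneaten one

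*Combined protocol and SAP*

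**What the plan says.** Section 7.2.2 (Energy Intake) sets out two methods.

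- **Formal food-intake days.** Food is offered in excess and weighed before and after the meal. In Part A, "A formal 24 h food intake study will be carried out on Part A from Cohort 3 onwards". The two windows are Day -1 and "Day 1 (measuring lunch and dinner on Day 1 and breakfast on Day 2"). In Part B the formal days are -1, 2 and 30.
- **All other days.** "For other days in Part A and Part B, energy intake will be carried out semiquantitatively": "clinical research unit staff will record the timing, types and amounts of food eaten by subjects", and at the end of each meal "the percentage of food left will be assessed to be either <10%, 10-<25%, 25-<50% or ≥50" per cent.

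Section 5.1.2 places the Part B doses on Days 1, 8, 15, 22 and 29. Section 5.2.3 gives the inpatient stays as Days -2 to 4, 8–9, 15–16, 22–23, 29–31 and 36–37. For Part A, section 5.1.1 states: "On Day 1 subjects will receive a single dose of Y14 or placebo by SC injection".

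Section 9.2.2 describes the derivation of energy intake by weighing only ("Each component of the meal will be weighed pre and post-meal") and does not say which days it covers. Section 10.5 provides for pharmacodynamic values to be listed and, where appropriate, summarised descriptively. It gives no rule for the bands. Food consumption under multiple dosing is an exploratory objective (section 4.3).

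**The concern.** Three of the four bands divide the lower half of the leftover scale, where the subject has eaten most of the meal. The fourth takes the whole upper half. A subject who ate 45% of lunch and one who ate none of it are coded alike. Section 3.1 says that Y14 was chosen partly for its anorectic effect, so the scale is coarsest where a strong effect would appear.

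This matters most for the second, third and fourth Part B doses. Days 2 and 30 follow the first and last doses. Between them, whether suppression holds, fades or builds rests on the semiquantitative record, because no other measure of food eaten is specified for stays 2–4. The satiety scale is a rating and does not measure intake. Detail that is not captured at the meal cannot be reconstructed later.

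**Working it through.** The plan gives no effect size, standard deviation or power for energy intake, so it has no figure to reproduce on this point. The planned enrolment agrees with the cohort structure: Part A 4 + 4×6 = 28; Part B 3×8 = 24.

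**1. Which dosing days are weighed?**

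- Part B: dosing days {1, 8, 15, 22, 29} and weighed days {-1, 2, 30} have no day in common. Of 24×5 = 120 planned administrations, 0 fall on a weighed day.
- Part B stays 2–4: Days 8–9, 15–16 and 22–23 contain no weighed day.
- Part A, active doses: Cohort 1 has 3 active × 3 periods = 9, and Cohorts 2–5 have 5 active × 4 = 20, total 29. Cohorts 1–2 have no formal study: 9 + 5 = 14 of 29.
- Part A including placebo: 4×3 + 6×4 = 36 administrations. Cohorts 1–2 account for 12 + 6 = 18, and the other 18 (Cohorts 3–5) are weighed on the dosing day.

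**2. How wide are the bands?** They span 10, 15, 25 and 50 percentage points of food left. The top band covers 0–50% eaten.

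**3. Where does the scale stop responding?** The documents give no intake distribution, so this step rests on assumptions. Let E be the fraction of the served meal eaten, normal with mean m(1−r) and SD 0.10, cut at 0 and 1. Here m is the fraction eaten without drug (0.95 or 0.80) and r is the reduction in intake. With bands scored 0 to 3, the expected score is P(E≤0.90) + P(E≤0.75) + P(E≤0.50).

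Example, m = 0.95 and r = 60%: the mean eaten is 0.95×0.40 = 0.38. The first two terms are 1.00 and the third is Φ((0.50−0.38)/0.10) = Φ(1.2) = 0.88, so the score is 2.88.

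| Reduction r | 0% | 20% | 40% | 60% | 80% | 100% |
|---|---|---|---|---|---|---|
| Score, m = 0.95 | 0.33 | 1.38 | 2.20 | 2.88 | 3.00 | 3.00 |
| Score, m = 0.80 | 1.15 | 1.94 | 2.58 | 2.96 | 3.00 | 3.00 |

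The score rises steadily up to a reduction of about 50–60% and is then at its ceiling. Beyond 60%, only 3.00−2.88 = 0.12 (m = 0.95) or 3.00−2.96 = 0.04 (m = 0.80) of the scale remains.

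**4. Would a split restore the distinction?** Compare r = 60% with r = 80% on the same assumptions.

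- Share of meals in the present ≥50% band: 88% against 99.9% (m = 0.95); 96% against 100% (m = 0.80).
- Share with ≥75% left, that is P(E≤0.25): for m = 0.95, Φ((0.25−0.38)/0.10) = Φ(−1.3) = 10% against Φ((0.25−0.19)/0.10) = Φ(0.6) = 73%. For m = 0.80, Φ(−0.7) = 24% against Φ(0.9) = 82%.

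A cut at 75% left separates two levels of strong suppression that the present code runs together.

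**The case against.** The case for leaving the record alone has force, and most of it limits the point without removing it.

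- **Dosing days in general.** A reader might infer that intake is never measured properly on a dosing day. That is not so: in Part A from Cohort 3 onwards, lunch and dinner on Day 1, the dosing day, are weighed. Cohorts 1–2 hold the lowest proposed doses (1–16 mg), and any of the eight optional cohorts would come under the weighed scheme. If all eight were added with 5 active subjects each (an assumption), the banded share would fall to 14 of 29 + 40 = 69, about 20%.
- **No measurement at all.** A reader might infer that the bands cannot measure appetite suppression. The table shows that they can, up to roughly half a meal. The plan states no expected effect, so nothing in it shows that Y14 will act in the saturated range. With a standard diet in the unit (section 5.2.3), fine bands at low leftovers are a sensible way to catch a modest effect.
- **The objective.** The exploratory comparison uses the weighed Days -1, 2 and 30 and does not depend on the bands.
- **Energy error.** It is tempting to score each band at its midpoint and quote the resulting error in energy. The plan never scores the bands or converts them to energy, so that error belongs to no planned analysis.
- **The nausea stopping criterion.** Section 5.1.4 refers to "Moderate nausea or vomiting that prevent subjects from eating a meal on 3 or more occasions", and a reader might take the leftover band as its source. Nothing says so. The criterion rests on judging an adverse event: section 7.3.2 requires events to be described in detail, and section 3.2 says nausea is detected by adverse event recording and questionnaires.
- **Section 9.2.2.** It might be read as saying that every meal is weighed. Read with section 7.2.2, the weighing belongs to the formal days, so this is a matter of clarity.
- **Amounts eaten.** Staff also record amounts of food eaten, which may show an untouched meal. The bands are the only stated scale for leftovers, however, and the Meal Manual and schedule of events are not in the text available, so any finer detail there could not be checked.

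What stands is that the top band is the coarsest, and that for doses 2–4 no weighed measure stands behind it.

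**Conclusion.** The point holds as a minor, inexpensive improvement. For all 120 planned Part B administrations (on the dosing day), for the whole of stays 2–4, and for 14 of 29 planned active Part A dosing occasions, leftovers are coded on a scale whose top category spans half of the range. The loss is confined to grading within strong suppression, above a reduction of roughly 50–60%, and to the course of such suppression across doses 2–4. The weighed exploratory comparison and the safety criteria are unaffected.

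The counts assume the planned cohorts, weekly dosing and the stated food-study days. Sections 5.1.5 and 7.2.2 allow the dosing interval and study days to change with emerging data. The saturation level depends on the assumed baseline intake (80–95% of the meal) and SD (0.10). That all meals with at least half left share one code needs no assumption.

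**What to change.** In section 7.2.2, keep the three lower bands and replace the top one with 50–<75%, 75–<100% and 100% left (meal not eaten). State in section 9.2.2 or 10.5 that semiquantitative meals are reported as ordered categories, with meals not eaten shown as their own category. Add one sentence to section 9.2.2 saying that weighed energy intake applies to the formal food-intake days.

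The cost is two more boxes on the meal form (six categories in place of four) and the matching wording. No extra visit, weighing or procedure is needed. If the Meal Manual already asks for a percentage or a not-eaten entry, it is enough to align the protocol text with it.
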